## SYNOPSIS

TITLE OF STUDY	Reducing catheter use: a randomised on the efficacy of an electronic reminder system
TRIAL REGISTRATION	Registration with the Australia New Zealand Clinical Trial Registry (ANZCTR) pending
PROTOCOL VERSION NUMBER	Version 1.0
SPONSOR/FUNDING BODY	This project is funded by an industry grant.
ROLES & RESPONSIBILITIES	
Chief Investigators:  [name]
 
[name]
 
[name]
 
[name]
 
A/[name]
 
Study team:  [name] (Project Manager)  [name] (Project Officer)

PRIMARY OBJECTIVES	
 
1. To determine the efficacy of an electronic reminder system in reducing urinary catheter usage.
 
2. To determine whether the CATH TAG has an effect on nurses' ability to deliver patient care.
 

STUDY DESIGN	Stepped wedge cluster randomised controlled trial
STUDY DURATION	24 weeks stepped-wedge control and intervention phases
NUMBER OF PARTICIPANTS	1 hospital
INCLUSION CRITERIA	
The hospital must have:
 
 
1. An intensive care unit.
 
2. More than 30,000 patient admissions per year.
 
3. 10 or more wards/units.
 

EXCLUSION CRITERIA	Hospitals will be excluded from the study if they do not meet any of the inclusion criteria.
INTERVENTION	The introduction of an electronic reminder system for removal of urinary catheters.
OUTCOME MEASURES	
OBJECTIVE 1
 
Primary outcome
 
 
1. Urinary catheter device utilization ratio (number of urinary catheter-days divided by the number of patient-days)
 
 
Secondary outcome(s)
 
 
1. The number of cases of catheter associated asymptomatic bacteriuria (CA-ASB) per 100 catheter days.
 

	
2. The number of urinary catheters inserted per 100 admissions
 
OBJECTIVE 2
 
Primary outcome
 
1. Perceptions of nurses about ease of use of the CATH TAG
 
Secondary outcome(s)
 
1. Perceptions of nurses about effectiveness of the CATH TAG
 
2. Perceptions of nurses regarding changes in ownership or interest by patients in catheter management.
 
3. Barriers to CATH TAG working successfully in varied types of patients

RECRUITMENT & ENROLMENT	The recruitment process will purposively invite eligible hospitals to participate through stakeholder and partner networks.
DATA COLLECTION	Data will be collected prospectively on the number of catheters being used during the control and intervention periods.
STATISTICAL ANALYSES	
Objective 1
 
Data analysis will be performed using the generalised estimating equations, with the duration of catheterisation as the dependent variable, and intervention as the independent variable.
 
Objective 2
 
Through an online survey and focus group the data analysis process will aim to investigate pre-determined themes reflected in the study's objectives as well as to identify emerging themes.

DISSEMINATION	The investigators will implement a dissemination plan that will include communication strategies for all stakeholders, a publication plan (to minimally include a protocol paper and primary outcomes papers) and presentations at national and international conferences.

## Abbreviations

ACIPC	Australasian College of Infection Prevention & Control
ACU	Australian Catholic University
ACSQHC	Australian Commission on Safety and Quality in Health Care
AMR	Antimicrobial resistance
ANU	Australian National University
ANZCTR	Australia New Zealand Clinical Trial Registry
APHA	Australian Private Hospitals Association
ASID	Australasian Society for Infectious Diseases
AVON	Avondale College of Higher Education
CA-ASB	Catheter associated asymptomatic bacteriuria
CAUTI	Catheter associated urinary tract infection
HAI	Healthcare associated infection
HAUTI	Healthcare associated urinary tract infection
HREC	Human Research Ethics Committee
ICU	Intensive care unit
NHMRC	National Health and Medical Research Council
QALY	Quality-adjusted life year
QUT	Queensland University of Technology
UniM	University of Melbourne
UTI	Urinary tract infection

## **Title**

Reducing catheter use: a randomised controlled study on the efficacy of an electronic reminder system

## **Trial Registration**

The trial will be registered with the Australia New Zealand Clinical Trial Registry (ANZCTR), (Registration pending).

## **Funding, sponsors and partners**

This project is led by the Avondale College of Higher Education. Avondale College will be responsible for managing the study design, conducting the intervention, data analysis and interpretation, publication and dissemination of results.

Academic project partners at Monash University and Deakin University will provide in-kind contributions to the study design, conduct, data analysis and interpretation and the publication and dissemination of results.

The project is being funded by an industry grant.

## **Background**

Indwelling urinary catheters are commonly used in healthcare facilities, with foundation work by two investigators indicating that 26% of patients admitted to an Australian hospital receive an indwelling urinary catheter and 1% of these patients develop catheter-associated urinary tract infections (CAUTIs). Healthcare associated urinary tract infections (HAUTIs), including CAUTIs have been associated with increased morbidity, mortality, higher hospital costs for patients and health systems. In Australia, an estimated 380,000 bed days are lost each year due to HAUTIs, a large proportion of which are CAUTIs. Urinary tract infections (UTIs), specifically CAUTIs are associated with higher risk of antimicrobial resistance (AMR), making the treatment of patients difficult and compounding the effects of AMR when treatment is provided. A recent high-level meeting of the United Nations General Assembly addressed the issue of increasing AMR. This further emphasises the need to develop interventions to reduce the incidence of CAUTIs.

Despite advances in infection prevention and control, CAUTIs remain problematic, hence further research is needed to identify ways to reduce the burden they create. The greatest risk factor for CAUTIs is prolonged catheterisation, with catheters often placed unnecessarily, lacking documented reasons for insertion, and catheters remaining in place too long and not being promptly removed. Interventions that prompt removal of unnecessary catheters may therefore enhance patient safety. A reminder intervention is a mechanism used to remind either a physician or nurse that the catheter is still in place and that removal may be warranted if the catheter is no longer required.

The CATH TAG is an electronic device that adhesively attaches to the catheter bag. It has a non-intrusive green light that flashes intermittently for a period of 24 hours upon activation. After 24 hours the green flashing light changes to red, flashing with increased rapidity and visibility. The light will flash red for 4 hours and subsequently change back to green, slower flashing, restarting the cycle. The red flashing light is an indication for the nurse to reassess the need for a urinary catheter and remove it when it is no longer required. This cycle will continue for 10 days and then change permanently to the red flashing light to indicate that the battery of the CATH TAG is exhausted.

Emerging AMR and the risks associated with it, the frequency of unnecessary catheter use, the increased costs for hospitals through increased bed days and the increased workload CAUTIs create for nurses in Australia and in hospital settings worldwide, highlight the need for novel methods to reduce urinary catheter use and the burden of CAUTIs.

## **Research Plan**

### ***Research aims***

Objective 1: To determine the efficacy of an electronic reminder system in reducing urinary catheter usage.

Objective 2: To determine whether the CATH TAG has an effect on nurses' ability to deliver patient care.

### ***Research hypotheses***

1. There is no difference in urinary catheter usage when using an electronic reminder system, as opposed to current practice.
2. The CATH TAG has no impact on nurses' ability to deliver patient care.

### ***Study design***

A stepped wedge cluster randomised controlled study will be undertaken in one hospital over a 24-week period (Figure 1). A mixed methods approach will be used, as the study includes a qualitative approach. The clusters in the study are pairs of individual hospital wards. The stepped wedge design includes an initial period where no wards are exposed to the intervention. Afterwards, at regular intervals (the "steps") two wards, forming one cluster, are randomised to cross over from the control to the intervention with the process continuing until all enrolled wards have crossed over. There will be a random sequential allocation of the intervention to the wards, i.e. each enrolled ward will be introduced to the intervention two at a time, approximately every 4 weeks until week 20, when all wards would have been exposed to the intervention. The study design enables each ward to act as its own control, which removes the potential for some confounders such as variations in ward size and case mix. Staggered commencement and duration of the intervention, supports feasibility while maintaining the rigour of the study. This design will allow research staff to work with individual wards as they change over, maximising consistency of the intervention and aiding implementation. In addition, data collection continues throughout the study, so that each cluster contributes observations under both control and intervention observation periods. In month 6 of the study, an online survey of nursing staff will be administered. Approximately two months after the stepped wedge study is completed, a focus group will be conducted.

Ward	1 month	2 months	3 months	4 months	5 months	6 months	Post study (2 months)
A + B	Blue (horizontal lines)	Green (vertical lines)	Green (vertical lines)	Green (vertical lines)	Green (vertical lines)	Green (vertical lines)	Survey  Focus group
C + D	Blue (horizontal lines)	Blue (horizontal lines)	Green (vertical lines)	Green (vertical lines)	Green (vertical lines)	Green (vertical lines)	
E + F	Blue (horizontal lines)	Blue (horizontal lines)	Blue (horizontal lines)	Green (vertical lines)	Green (vertical lines)	Green (vertical lines)	
G + H	Blue (horizontal lines)	Blue (horizontal lines)	Blue (horizontal lines)	Blue (horizontal lines)	Green (vertical lines)	Green (vertical lines)	
I + J	Blue (horizontal lines)	Blue (horizontal lines)	Blue (horizontal lines)	Blue (horizontal lines)	Blue (horizontal lines)	Green (vertical lines)	

Blue (horizontal lines) = control; Green (vertical lines) = intervention

Figure 1. Study design overview

### Setting and eligibility

#### Population

One Australian hospital will be enrolled in the study.

#### Eligibility criteria for hospitals

To be eligible to participate and include patients in the trial, the hospital must have:

- An intensive care unit
- More than 30,000 patient admissions per year
- Ten or more wards/units

#### Exclusion criteria for hospitals

Hospitals will be excluded from the study if they do not meet any of the inclusion criteria. Potential wards and units eligible for inclusion are medical wards, surgical wards and intensive care units.

Day-stay units and psychiatric wards will be excluded. Neonates (<2 years old) may be excluded if the CATH TAG is too large for the catheter tubing or interferes with patient care.

#### Areas of hospital inclusion and exclusion criteria

The study will involve at least ten wards or units within a hospital.

### *Recruitment of hospitals*

The recruitment process will purposively invite eligible hospitals to participate through stakeholder and partner networks. The first confirmed hospital will be accepted. Patient level consent will not be obtained or be required, given the nature of the study and study design. There is no patient intervention or involvement, rather an addition to existing procedures regarding catheter removal.

### *Other considerations*

Hospitals could be excluded from the study if within the study time frame they are:

- undertaking a project that may influence the outcomes measured in this study
- opening, closing or relocating

### *Recruitment of participants (nurses) for survey and focus group*

In order to recruit nurses to participate in an online survey, information leaflets will be distributed to each participating ward during month 6 of the study. If possible (e.g. approved by the hospital) the same information will be sent to nurses via email. Other communication methods such as a ward communication diary, reminder at a staff meeting or during handover may also be used. Nurses have been chosen as the participants as they have the primary role in day to day indwelling catheter management and care.

The information leaflet/email will contain details about the survey and a web link (presented as URL and alternatively as QR code) to participate. Upon commencement of the survey, information regarding the study will be provided, in addition to a consent form. To improve response rates, an incentive of ten \$50 gift cards will be made available and will be allocated at random to those who complete the survey. To enter the draw for a gift card, participants will need to click on a different web link, provided at the end of the survey. This will ensure that no personal details are linked to the survey.

To recruit participants for a focus group, interest can be registered at the end of completing the online survey. To register interest, participants will need to click on a different web link, provided at the end of the survey. This will ensure that no personal details are linked to the survey. Focus group participants will receive a \$100 gift card to compensate them for their time. If more people register for the focus group than are required, purposive sampling will occur to ensure a representative sample of different wards. If it remains such that there are still too many registered than can be enrolled, they will be chosen at random. The focus group will be conducted 2 months after completion of the intervention (month 8 of the study). Prior to or on the day of the focus group, information regarding the study will be provided, in addition to obtaining informed consent.

### *Discontinuation of study or study site*

The study will be discontinued if a regulatory body, funding body, or Human Research Ethics Committee (HREC) judges it necessary for medical, safety, regulatory, or other reasons consistent with applicable laws, regulations and good clinical practice.

### ***Randomisation and blinding***

Wards in the hospital will be randomly assigned to cross over to the intervention every four weeks over the trial duration of 24 weeks. All included wards will be provided with sufficient notice of the dates to cross over to the intervention. Computer-generated randomisation of the cross over dates for the wards will be performed independently by one of the investigators, who will not be involved in assessment or delivery of the intervention. Wards will not be blinded because it is not feasible to blind staff to the intervention.

### ***Control phase***

During the control phase, usual practice regarding catheter care and removal will occur, according to local policy or process guides. No electronic or alert systems for catheter removal will be used.

### ***Intervention***

After four weeks, two wards will cross over to the intervention. The intervention is the use of the CATH TAG. A CATH TAG will be attached to each catheter. When the CATH TAG is attached to a catheter bag it will initially flash green for a set period of 20 hours. After 20 hours the green flashing light will cease and a red light will flash with increased rapidity for four hours, alerting nurses to review the patients indwelling catheter. After 4 hours the red fast flashing light will change back to the more slowly green flashing light, restarting the cycle until the catheter is removed. There is no option for nurses to manipulate the flashing light or amend the flashing cycle.

For patients who are transferred from a control ward to an intervention ward, a CATH TAG will be attached to their catheter upon transfer. Data collected up to the date of transfer will contribute to the control (ward) dataset. Following transfer, data will be contributed to the intervention (ward) dataset.

For patients who are transferred from an intervention ward to a control ward, the CATH TAG will be removed upon transfer. Data collected up to the date of transfer will contribute to the

intervention (ward) dataset. Following transfer, data will be contributed to the control (ward) dataset.

### ***Implementing the intervention***

In the week prior to the intervention commencing, information sessions about the study will be provided to the participating hospital and staff. A variety of methods will be used to further alert staff and raise awareness about the intervention prior to it being rolled out. These methods include placing wall posters in wards and key locations, handing out flyers and information leaflets as well as branded promotional material, such as pens. Nurses will be trained in using the CATH TAG.

### ***Confounders***

Potential confounders include the different staff inserting and caring for patients with an indwelling catheter and the indications for urinary catheterisation. The cluster randomised design of this study minimises many of these issues, as wards (clusters) act as their own control. Further, there is no reason to suggest a fundamental change in the control and intervention periods for these variables. Duration of the intervention might have a confounding effect on the outcome variables and will be accounted for in data analysis.

Clinical staff working on a casual basis or across wards have the potential to provide responses to the survey or focus group from a range of perspectives, based on their experiences on different wards. To minimise this, the survey will focus the respondent to experiences in one particular area and obtain details about their exposure to working in different wards/hospital units.

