## ***Data collection***

*Objective 1: To determine the efficacy of an electronic reminder system in reducing urinary catheter usage*

Data will be collected by a specific staff member at the hospital, supported by the research team. Where data collection results in an increase in workload for the hospital staff (e.g. not part of usual practice), the research team will provide additional resources in the form of funding to account for additional hours for existing staff members or employment of new staff members for the purpose of data collection. The research team will provide the hospital staff member(s) with training about the project, data collection processes and data collection tools, as well as ongoing on-site and telephone support. For the purpose of this protocol, the dedicated hospital staff member(s) will be referred to as hospital personnel.

The figure below (Figure 2) summarises the data collection process with further details provided below.

*Figure 2.* Overview of the data collection process

Hospital personnel will prospectively collect data five days a week on participating hospital wards, during both control and intervention periods. Hospital personnel will visit inpatient areas and patients who receive an indwelling urinary catheter will be identified and followed-up until discharge or catheter removal. Hospital personnel will check that a CATH TAG has been attached to every catheter, on wards that have crossed over to the intervention. The following information will be collected: hospital number, age, sex, date of admission, date and time of catheter insertion, reason for censoring follow-up, date of discharge or catheter removal, designation of person

inserting the catheter, ward and allocation to control or intervention ward. A review of microbiology results will be undertaken by the hospital personnel for each person who receives a catheter and has a urinary sample taken. If a person has a positive urine culture after catheterisation and prior to removal, the following will be collected: data of specimen collection, organism(s) isolated, colony forming units, white cell count.

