### ***Data analysis***

*Objective 1: To determine the efficacy of an electronic reminder system in reducing urinary catheter usage.*

The primary outcome measure is the duration of catheterisation, and the study aims to evaluate the effect of the intervention. The analysis will be performed using the generalised estimating equations, using the duration of catheterisation as the dependent variable and intervention as the independent variable. Duration of the intervention will be treated as a confounding variable. It is anticipated that duration of catheterisation will be normally distributed, but exploratory analyses (and where necessary transformation) will be performed. Robust standard errors will be used to adjust for correlation at ward level and autocorrelation in time. There is no expected delay in the effect of the intervention on the outcome.

*Objective 2: To determine whether the CATH TAG has an effect on nurses' ability to deliver patient care.*

Survey:

Data from the anonymous online survey will be analysed using SPSS. It is anticipated that data will be normally distributed but exploratory analyses will be performed, including testing of assumptions of linearity, homoscedasticity, multicollinearity and normality of errors and if necessary transformation of data. Validity and reliability will be examined. Subsequently a general satisfaction score and individual satisfaction scores for the four dimensions of nurses' experiences with the CATH TAG (Ease of use, Effectiveness, Changes in ownership, Barriers) will be calculated. Regression analysis will be conducted to determine if the duration of the intervention or the ward nurses primarily work on had an effect on nurses' experiences with the CATH TAG.

Any problems reported in the open questions will be taken into the focus group to be discussed and subsequently analysed qualitatively (see below).

Focus group:

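### Indication is named as a confounder but never recorded, and age, sex and inserter designation are recorded but absent from the stated catheter-duration model

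*Protocol*

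**What the plan says.** The Confounders section of the protocol names two sources of confounding: "Potential confounders include the different staff inserting and caring for patients with an indwelling catheter and the indications for urinary catheterisation". It gives two reasons for not being troubled by them. The first is the design: "The cluster randomised design of this study minimises many of these issues, as wards (clusters) act as their own control". The second is an assumption of stability: "there is no reason to suggest a fundamental change in the control and intervention periods for these variables".

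The Objective 1 analysis is a generalised estimating equation, "using the duration of catheterisation as the dependent variable and intervention as the independent variable". The Synopsis gives the same two terms. Data analysis adds one more: "Duration of the intervention will be treated as a confounding variable". No other covariate is mentioned.

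The data list in the Data collection section begins "hospital number, age, sex, date of admission, date and time of catheter insertion, reason for censoring follow-up" and goes on to the end date of follow-up, the inserter's designation, ward and allocation. Table 3 repeats these items (with date of birth in place of age) and marks date of birth, sex and inserter designation for use in data analysis. Neither list has a field for why the catheter was placed. The only reason recorded is the reason for censoring. Caring staff, named in the same sentence as inserting staff, are not recorded either.

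**The concern.** The protocol names a variable as a possible confounder, relies on it being stable between control and intervention periods, and then does not record it. That differs from leaving a covariate list to an analysis plan. An analysis plan can choose among the collected fields, but it cannot describe, check or adjust for a field that is not on the spreadsheet.

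The own-control argument covers stable differences between wards. It does not cover change over time within a ward, where the control and intervention data come from different patients. Every ward moves from control to intervention, so control data are earlier and intervention data later. The mix of indications could also shift because of the intervention. The Background says catheters are often placed without need, ward staff are unblinded, and the number of catheters inserted per 100 admissions is itself a secondary outcome. If fewer marginal catheters were placed once tags were in use, mean duration could move without any change in how promptly catheters are removed.

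A smaller loss is that age and sex, already collected, could absorb some patient-to-patient variation in duration at no cost, but the stated model does not use them.

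**Working it through.** **Step 1. Named, collected and modelled variables, side by side.**

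| Variable | Named as confounder | Collected | In stated model |
|---|---|---|---|
| Indication | yes | no | no |
| Inserting staff | yes | yes (designation) | no |
| Caring staff | yes | no | no |
| Age, sex | no | yes | no |
| Duration of intervention | yes | derivable from ward and dates | yes |

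The Data collection overview figure is not available here. The text says it summarises the process and that details follow, and those details contain no indication field.

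**Step 2. The protocol's own power figure.** Inputs from Sample size: 10 wards, two crossing over each month, 6 months, 35 catheterised patients per ward per month, 50% against 40% in situ on day 4, correlation 0.1, significance level 0.05 (taken as two-sided).

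N = 10 × 6 × 35 = 2100, as stated.

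The Hussey-Hughes variance, which includes period effects, is

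Var = I·s²·(s² + T·τ²) / [(I·U − W)·s² + (U² + I·T·U − T·W − I·V)·τ²]

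with I = 10, T = 6, U = 30, W = 220, V = 110. So I·U − W = 80 and the second bracket is 900 + 1800 − 1320 − 1100 = 280.

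At the mean proportion 0.45, the total variance is 0.45 × 0.55 = 0.2475. With 0.1 read as an intraclass correlation, τ² = 0.02475 and the within-ward variance is 0.22275, so s² = 0.22275/35 = 0.006364.

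Var = 10 × 0.006364 × (0.006364 + 0.1485) / (80 × 0.006364 + 280 × 0.02475) = 0.001325; SE = 0.0364.

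Power = Φ(0.10/0.0364 − 1.96) = 78.4%.

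Other choices of proportion for the variance give 78.0% to 79.7%. Reading 0.1 as a between-ward coefficient of variation (τ = 0.1 × 0.5) gives 80.9% to 82.3%. The stated 81% is therefore reproduced to within about 2 points under some standard readings. The calculation is unadjusted and uses no covariates.

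**Step 3. What adjustment might add.** The documents do not say how much variance these covariates explain. Assume a share R² of the within-ward variance and replace s² by s²(1 − R²). Two cluster-period sizes are shown: 35, and 32.2, which is 35 per calendar month scaled to a four-week step (35 × 28/30.44).

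| R² (assumed) | Power, 35 per period | Power, 32.2 per period |
|---|---|---|
| 0 | 78.4% | 75.1% |
| 5% | 80.4% | 77.2% |
| 10% | 82.4% | 79.3% |

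The gain is about 2 points at 5% and 4 points at 10% in either column.

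**Step 4. Limits of this sum.** It is on the binary day-4 endpoint used for sample size, whereas the covariates would enter a model for duration. It says nothing about bias, which depends on how far case mix shifts within wards, and the documents give no figure for that.

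**The case against.** Covariate lists are commonly left to an analysis plan, and one may exist. Age, sex and inserter designation are being collected, so such a plan could use them. A table entry marking them for data analysis does not promise adjustment; it could mean description or subgroups. This stands, and it makes the unused-covariate half of the point an improvement rather than a contradiction. It does not reach indication, which no plan can use unless it is recorded.

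The omission is also reasoned. A reader might infer that the protocol declares these variables to need no handling. It does not: it says the design reduces many of the issues and that no fundamental change is expected. The difficulty is that, for indication, this expectation cannot be tested.

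A reader might also infer selective enrolment by unblinded staff. The documents do not support that: individual consent is not sought, and catheterised patients on participating wards are identified and followed as they arise. What remains is a possible change in who is catheterised.

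It is further objected that drift common to all wards calls for a calendar-period term, not patient covariates, and that indication and inserter arise after allocation, so routine adjustment for them could itself distort the effect. Both objections stand, and they limit the remedy. The covariates also exist only for catheterised patients, so they cannot adjust the Table 2 primary outcome, catheter-days per patient-day.

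**Conclusion.** The point holds as a low-cost improvement to the catheter-level duration model. Two facts are plain from the text: indication is named as a confounder and not recorded, and the stated model uses none of age, sex or inserter designation although all three are collected. The first matters more, because it is fixed once data collection starts without the field.

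The likely precision gain is small, about 2 to 4 power points, and rests on an assumed R² of 5% to 10% and on the binary day-4 endpoint. The 75.1% starting value in one column comes from the four-week rescaling and should not be read as the effect of omitting covariates. Nor do the documents show that the treatment effect would be biased; they show only that one of the protocol's stability assumptions could not be examined. The absence of a stated calendar-period term is a separate matter that this point neither covers nor resolves.

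**What to change.** 1. In the Objective 1 section of Data analysis, and in the Synopsis, name age and sex as prespecified fixed covariates in the catheter-duration model.
2. Add one coded field for indication to the spreadsheet and to Table 3, taken from the medical notes already being read, with an explicit undocumented category.
3. Prespecify a table of indication and inserter designation by control and intervention period, so that the stability assumption in the Confounders section can be checked.
4. Prespecify a sensitivity analysis of the duration model that also adjusts for indication and inserter designation. Keep both out of the main model because they arise after allocation and could be affected by the intervention.
5. State that these covariates apply to the catheter-level duration model only, and that they do not stand in for a calendar-period term.

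The cost is a few sentences of model wording and one spreadsheet column, which should be in place before data collection begins. The main downside is incomplete data: the Background itself notes that documented reasons for insertion are lacking, so the undocumented category may be sizeable and should be reported by period.
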